a: An interruption of lenvatinib for more than 28 days (due to treatment-related toxicities) will require discussion with the sponsor before treatment can be resumed. During treatment interruption, repeat AEs assessment about every 7 days (until restarting administration).

b: Initiate optimal medical management for nausea, vomiting, diarrhea, and/or hypothyroidism prior to interruption or dose reduction of lenvatinib.

c: Not applicable to abnormal clinical laboratory values that are not clinically significant based on the judgment of the investigator or subinvestigator.

d: Grade 2 toxicities will be determined to be tolerable or intolerable by both the subject and investigator or subinvestigator.

e: Obese subjects with weight loss do not need to return to baseline or Grade 1 weight loss to restart lenvatinib. There should be no weight loss for at least 1 week, and subjects should be started at the lower dose.

f: For asymptomatic Grade ≥ 3 elevations of amylase and lipase, sponsor should be consulted to obtain permission to continue treatment.

g: Excluding laboratory abnormalities judged to be nonlife-threatening, which should be managed as Grade 3.

Table 3 Dose Reduction Recommendations for Lenvatinib

Initial Lenvatinib Dose (mg, QD)	Adjusted Dose To Be Administered (mg, QD)		
	Reduction 1	Reduction 2	Reduction 3
12	8	4	4QOD ^a
8	4	4QOD ^a	

a: 4 mg every other day [QOD]. Any dose reduction below 4 mg every other day must be discussed with the sponsor.

9.4.1.3.2.2 Criteria for Delay of Treatment, Resumption, and Discontinuation of Nivolumab

9.4.1.3.2.2.1 Criteria for Delay of Treatment and Resumption of Nivolumab

Dose adjustments for management of intolerable toxicities will be made according to the guidelines shown in Table 4.

Table 4 Dose Delay and Resuming Dosing of Nivolumab

Treatment-Related Toxicity ^a	Dose Delay Criteria	Criteria to Resume Dosing
Skin-related adverse event	Grade 3	Grade \leq 1 or baseline value
Fatigue	Grade 3	Grade \leq 2
Laboratory abnormality (except for AST/ALT)	Grade 3 (except for amylase or lipase abnormalities that are not associated with symptoms or clinical manifestations of pancreatitis)	Grade \leq 1 or baseline value (T-Bil: baseline CTCAE Grade or normal)
AST/ALT	Baseline AST/ALT is within normal limits: Grade \geq 2. Baseline AST/ALT is Grade 1: Grade \geq 3. Baseline AST/ALT is Grade 2: \geq two-fold of baseline value or \geq 8x ULN	Baseline CTCAE Grade or normal

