3.2.3.2 Treatment Period

In the Treatment Period, subjects will receive lenvatinib in combination with nivolumab. The Treatment Period will begin with the first dose of study drug administration on Cycle 1

Day 1. Each cycle is 28 days long and subjects continue treatment until they meet any of the criteria in “Discontinuation Criteria by Subject (see [Protocol Section 9.3.3.1](#))”.

Subjects will be hospitalized during the Cycle 1, however, outpatient is allowed after Cycle 1 Day 15, when investigator or subinvestigator judges that that the subject’s safety is ensured.

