For lenvatinib, the number (percentage) of subjects who experienced a dose reduction and interruption will be summarized. For subjects who experienced a dose reduction, cycle of the first dose reduction will be summarized by descriptive statistics. Cycle of the first dose interruption will also be summarized in subjects who experienced a dose interruption. Frequency of dose reductions will be summarized by categories (1, 2, 3, ≥ 4). Frequency of dose interruptions will also be summarized by appropriate categories (e.g., 1, 2, 3, ≥ 4).

The date of dose reduction (from XX mg to YY mg, $XX > YY > 0$) is defined as the first date of planned dose of 0 mg followed by YY mg. The first date of 0 mg has to follow planned dose of XX mg. If the starting dose of YY mg does not follow 0 mg but XX mg, the first date of planned dose of YY mg is regarded as the date of dose reduction. Note that from 4 mg QD to 4mg QOD is also dose reduction.

The dose interruption is defined as the case where planned dose is 0 mg. The starting date of dose interruption is defined as the first date of planned dose of 0 mg following and followed by same dose level (> 0 mg). For example: 12 mg followed by 0 mg and followed by 12 mg; 8 mg followed by 0 mg followed by 8 mg. Successive days with planned dose of 0 mg is counted as one dose interruption event. If after dose 0 mg, the subject discontinued from lenvatinib permanently, it is not regarded as a drug interruption (but as a drug discontinuation).

An illustration for dose reduction and interruption in a subject is shown in Figure 2.

[figure not shown]

Figure 2 Dose reduction and interruption for lenvatinib

For nivolumab, the number (percentage) of subjects who experienced a dose interruption will be summarized. Cycle of first dose interruption will be summarized by descriptive statistics in subjects who experienced a dose interruption. Frequency of dose interruptions will be summarized by appropriate categories (e.g., 1, 2, 3, ≥ 4).

The dose interruption is defined as the case where planned dose of 0 mg. Successive dates with planned dose of 0 mg is counted as one dose interruption event, and the first date with

planned dose of 0 mg is defined as the starting date of dose interruption. If after dose 0 mg, the subject discontinued from nivolumab permanently, it is not regarded as a drug interruption (but as a drug discontinuation).

Subject data listings will be provided.

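### If off-days at 4 mg every other day are recorded as planned 0 mg, SAP 5.6.1 counts each one as a separate lenvatinib interruption

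*SAP*

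**What the plan says.** SAP 5.6.1 (Extent of Exposure) builds the lenvatinib interruption count from four statements:

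- Definition: "The dose interruption is defined as the case where planned dose is 0 mg".
- Start date: the "first date of planned dose of 0 mg following and followed by same dose level (> 0 mg"). The worked examples are 12 mg, 0 mg, 12 mg and 8 mg, 0 mg, 8 mg.
- Merging: "Successive days with planned dose of 0 mg is counted as one dose interruption event".
- The only exemption: "If after dose 0 mg, the subject discontinued from lenvatinib permanently, it is not regarded as a drug interruption".

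Three outputs use this rule: the number and percentage of subjects with an interruption, the cycle of first interruption, and a frequency table ("Frequency of dose interruptions will also be summarized by appropriate categories", with 1, 2, 3 and ≥4 as the example).

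Protocol Table 3 (section 9.4.1.3.2.1) places QOD at Reduction 2 for subjects starting on 8 mg and at Reduction 3 for those starting on 12 mg. Its footnote reads "4 mg every other day [QOD]. Any dose reduction below 4 mg every other day must be discussed with the sponsor". SAP 5.6.1 does mention this level, but only in the reduction paragraph: "Note that from 4 mg QD to 4mg QOD is also dose reduction". The interruption paragraph has no matching note. Both SAP versions in the file carry the same wording.

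**The concern.** Written out by day, QOD dosing is 4, 0, 4, 0, 4 mg. Each off-day then sits between two equal non-zero doses, the same pattern as the SAP's 12-0-12 example. Off-days are never consecutive, so the merging rule does not combine them, and the discontinuation exemption does not apply.

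The note on QOD in the reduction paragraph shows that the authors had the level in mind. It was needed there because a rule comparing mg amounts cannot see a step from 4 mg daily to 4 mg on alternate days. The interruption rule has a similar blind spot and was left without a note.

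At stake is whether the interruption summaries describe withheld treatment or simply the assigned schedule. A reader of the frequency table could take a subject in the ≥4 row as poorly tolerant when no dose had been withheld.

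**Working it through.** **Inputs.** The interruption rule, merging rule and exemption come from SAP 5.6.1. The QOD level comes from Protocol Table 3. The cycle length comes from SAP 3.2.3.2 ("Each cycle is 28 days long"). Group sizes come from SAP 3.2.1 and 3.2.2: 6 subjects in Part 1, 20 in Part 2, and at least 5 per weight group in Part 2. The documents give no interruption count to reproduce, so the rule is first tested on simple patterns, including the SAP's own example.

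**Rule as a formula.** Take each run of one or more consecutive planned 0 mg days. Count 1 if the planned dose just before the run equals the planned dose just after it and is above 0. Otherwise count 0.

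| Planned sequence (mg) | Count | Reading |
|---|---|---|
| 12-0-12 | 1 | interruption, as in the SAP example |
| 8-0-0-8 | 1 | consecutive days merged |
| 12-0-8 | 0 | dated as a reduction |
| 8-0-0, then permanent stop | 0 | discontinuation |

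**Uninterrupted QOD cycle, off-days coded 0 mg.** Doses fall on odd days and off-days on even days, giving 28 / 2 = 14 off-days. Off-day 2k is flanked by 4 mg on days 2k − 1 and 2k + 1.

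- For k = 1 to 13 both flanking days lie inside the cycle: 13 events.
- For k = 14 the flanking dose is on Day 29: 14 events if dosing continues, 13 if treatment ends on the last off-day.
- The k-th event falls on Day 2k, so the fourth is on Day 8, confirmed by the dose on Day 9.
- Over continuous cycles the count is 14 × 2 = 28 after two and 14 × 6 = 84 after six.
- The number of true interruptions is 0 throughout.

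**QOD with one real hold.** Suppose doses are taken on Days 1, 3, 5, 7 and 9, treatment is withheld on Days 11 to 17, and QOD resumes on Day 18 and runs to a dose on Day 34. The literal rule counts off-days 2, 4, 6 and 8 (4 events), the run from Day 10 to Day 17 (1 event), and off-days 19, 21, ..., 33 (8 events): 4 + 1 + 8 = 13. The true count is 1.

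**Effect on each output.**

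- Frequency table: inflated for any subject on QOD.
- Number (%) with an interruption, and cycle of first interruption: changed only if the subject had no true interruption before QOD. This is possible. Protocol Table 2 lets the dose be reduced for intolerable Grade 2 events without a hold, and the SAP dates a hold that restarts at a lower dose as a reduction.
- Size per such subject: 1/20 = 5 percentage points in Part 2, 1/5 = 20 points in a weight group at its minimum size, and 1/6 = 16.7 points in Part 1.

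**Not affected.** Lenvatinib dose intensity is total mg over days of treatment and does not use the interruption definition. DLTs and TEAEs leading to interruption are derived separately.

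**The case against.** The strongest reply is that the error depends on a data structure that cannot be seen. The rule works on planned dose and dose level. Table 3 lists QOD as one adjusted level, and the SAP's reduction note also treats it as a level in its own right. If the study medication data hold 4 mg QOD as one continuous non-zero record, an off-day is not a planned 0 mg day and the count is zero. SAP Figure 2, which illustrates reductions and interruptions, is not shown, and SAP section 9 places the derivation and dataset rules in separate documents. This stands, and it makes the point conditional. It does not remove it, because the visible rule is stated by date and in mg, and nothing in it excludes the daily reading.

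A reader might also infer more than the documents support:

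- *That a primary endpoint is compromised.* SAP 5.1.1 lists DLTs, AEs, laboratory tests, vital signs, ECG, ECOG-PS and LVEF. Interruption counts are exposure descriptives that support the tolerability objective.
- *That every subject on QOD shifts the percentage interrupted.* Only those with no earlier true interruption do.
- *That a comparison of 8 mg with 12 mg is biased.* The two groups are displayed side by side and the 8 mg group reaches QOD one step sooner, so the error could fall unevenly. However, SAP 5.3.3 and 5.3.4 plan no statistical comparison and no subgroup analysis.

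Subject listings are also planned, and a subject with 14 interruptions per cycle would probably be noticed. That makes detection likely but does not define the correct count.

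**Conclusion.** The point holds conditionally. If QOD off-days are carried as planned 0 mg, the rule in SAP 5.6.1 reports correct dosing as 13 or 14 interruptions per 28-day cycle, and such a subject meets the example ≥4 category by Day 8 (confirmed on Day 9). If QOD is carried as one non-zero level, the false count is 0. The documents do not say which applies, nor how many subjects reach QOD, so the effect on the Part 2 percentage runs from none to 5 points for each QOD subject with no earlier true interruption. The 20-point figure applies only to a weight group of exactly 5. This is a gap in the definition of a supportive output and does not threaten the trial's main conclusions. It is still worth closing because the rule as written can misclassify correct dosing and the remedy costs almost nothing.

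**What to change.** Add to the interruption paragraph of SAP 5.6.1:

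> *Scheduled non-dosing days at 4 mg QOD (or any less frequent agreed schedule) are part of that dose level and do not by themselves constitute planned dose 0 mg. At such a level an interruption starts on the first scheduled dosing day whose planned dose is changed to 0 mg; consecutive withheld scheduled dosing days, together with the off-days between them, count as one interruption event.*

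Apply it to the number (%), the frequency table and the cycle of first interruption. The second sentence matters for two reasons. It keeps the SAP's planned-dose basis, so a forgotten dose is not an interruption on QOD when it would not be one on daily dosing. It also prevents one hold from being split: scheduled dosing days on QOD are never adjacent, so withholding Days 3, 5 and 7 would otherwise count as three events.

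Check the dataset specification at the same time. If it already carries QOD as a level, the added text simply documents that. The cost is two sentences and one programming condition, with no new data. This is an analysis definition only and changes no dosing rule.

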5.6.2 Dose Limiting Toxicity

The number and percentage of subjects with DLT will be calculated. DLT will also be summarized per type of toxicity.

Subject data listings will be provided.

5.6.3 Adverse Events

The AE verbatim descriptions (investigator terms from the CRF) will be classified into standardized medical terminology using the Medical Dictionary for Regulatory Activities (MedDRA version 20.1 or later). Adverse events will be coded to the MedDRA lower level term (LLT) closest to the verbatim term. The linked MedDRA preferred term (PT) and primary system organ class (SOC) will also be captured in the database.

A treatment-emergent adverse event (TEAE), defined in the [section 8.3](#), will be included in summary tables. All AEs, treatment emergent or otherwise, will be presented in subject data listings.

Treatment-related TEAEs include those events considered by the investigator to be related to study treatment.

A subject will be counted only once within a SOC and PT, even if the subject experienced more than 1 TEAE within a specific SOC and PT.

An overview table, including the incidence of and the number of subjects with TEAEs, Treatment-related TEAEs, TEAEs with grade 3 or above, serious adverse events (SAEs), deaths, and TEAEs that led to discontinuation of lenvatinib, discontinuation of nivolumab, dose reduction of lenvatinib, dose interruption of lenvatinib and dose interruption of nivolumab will be provided.

The incidence of below events will be reported as the number (percentage) of subjects with TEAEs by MedDRA SOC and PT.

- TEAEs (any grade)
- TEAEs by the highest CTCAE grade
- TEAEs grade 3 or above
- Treatment-emergent SAEs
- Non-serious TEAEs
- Treatment-related TEAEs
- Treatment-related TEAEs by the highest CTCAE grade
- Treatment-related TEAEs grade 3 or above
- Treatment-related serious TEAEs

- TEAEs leading to discontinuation of lenvatinib
- TEAEs leading to dose reduction of lenvatinib
- TEAEs leading to dose interruption of lenvatinib
- TEAEs leading to discontinuation of nivolumab
- TEAEs leading to dose interruption of nivolumab

All deaths will also be summarized by primary reasons of deaths (progressive disease, AEs, others), deaths within 30 days of last dose of study drug, deaths >30 days of last dose of study drug, and treatment-related deaths.

Subject data listings of all deaths, SAEs, AEs leading to death, discontinuation of lenvatinib, discontinuation of nivolumab, dose reduction of lenvatinib, dose interruption of lenvatinib and dose interruption of nivolumab will be provided.

Select Adverse Events

The select Adverse Events (select AEs) consist of a list of MedDRA PT grouped by specific category (e.g. endocrine events, and gastrointestinal events categories, etc.). AEs that may differ from or be more severe than AEs caused by non-immunotherapies and AEs whose early recognition and management may mitigate severe toxicity are included as select AEs. The select AEs and the categories/sub-categories are defined by the Sponsor and the list of PT used for the analyses will be prepared separately from SAP.

Select AEs will be summarized by PT on each category/subcategory. The incidence of below events will be reported as the number (percentage) of subjects.

- Select AEs (any grade)
- Select AEs by the highest CTCAE grade
- Select AEs grade 3 or above
- Serious select AEs (any grade)
- Serious select AEs grade 3 or above
- Treatment-related select AEs (any grade)
- Treatment-related select AEs by the highest CTCAE grade
- Treatment-related select AEs grade 3 or above
- Treatment-related serious select AEs (any grade)
- Treatment-related serious select AEs grade 3 or above
- Select AEs leading to discontinuation of nivolumab (any grade)
- Select AEs grade 3 or above leading to discontinuation of nivolumab
- Select AEs leading to dose interruption of nivolumab (any grade)
- Select AEs grade 3 or above leading to dose interruption of nivolumab

Subject data listings of the select AEs will be provided.

5.6.4 Laboratory Values

Laboratory results will be summarized using Système International (SI) units. For all quantitative parameters, the actual value and the change from baseline to each postbaseline visit will be summarized by visit using summary statistics. Qualitative parameters will be summarized by number and percentage of subjects, and changes from baseline to each postbaseline visit will be reported using shift tables. Percentages will be based on the number of subjects with both nonmissing baseline and relevant postbaseline results.

Box plot display will be used to show the longitudinal change of the parameters by visit.

Laboratory test results will be assigned a low/normal/high (LNH) classification according to whether the value is below (L), within (N), or above (H) the laboratory parameter's reference range. The result of LNH classification will be provided in a subject data listing.

Laboratory parameters will be graded by CTCAE ver. 4.03 in the [section 13](#). Changes from CTCAE grade at baseline to each postbaseline visit and worst postbaseline will be reported using shift tables. CTCAE will also be used to identify subjects with Treatment-emergent markedly abnormal laboratory value (TEMAV). The number (percentage) of subjects with TEMA (markedly abnormal high/low) will be summarized for each visit and overall study period. The TEMA will be defined in the [section 8.3](#).

Subject data listings will be provided.

5.6.5 Vital Signs

Summary statistics for vital signs parameters (diastolic and systolic blood pressure, pulse, and temperature), weight, and SPO₂ and changes from baseline will be presented by visit.

Box plot display will be used to show the longitudinal change of the parameters by visit.

Subject data listings will be provided.

5.6.6 Electrocardiograms

The results of ECG assessments performed at each visit will be evaluated. Summary statistics for ECG parameters (Heart Rate, RR, PR, QRS, QT, and QTcF) and changes from baseline will be presented by visit.

Shift tables will present changes from baseline in ECG interpretation (categorized as normal; abnormal, not clinically significant; and abnormal, clinically significant) to each visit.

In addition, the number (percentage) of subjects who met below criteria at least once in QTcF will be presented:

Absolute QTcF interval prolongation:

- QTcF interval >450 ms
- QTcF interval >480 ms
- QTcF interval >500 ms

Change from baseline in QTcF interval:

- QTcF interval increases from baseline >30 ms
- QTcF interval increases from baseline >60 ms

Subject data listings will be provided.

5.6.7 Other Safety Analyses

LVEF

Descriptive statistics for LVEF and LVEF changes from baseline assessed by MUGA scans or echocardiograms will be summarized by visit.

Subject data listings will be provided.

ECOG PS

The number (percentage) of subjects for each category of ECOG PS will be summarized by visit. The highest postbaseline scale of ECOG PS for each subject will also be summarized.

Subject data listings will be provided.

5.7 Other Analyses

Immunogenicity

Serum anti-nivolumab antibodies (ADA) will be summarised for subjects which meet all the following criteria.

- Nivolumab is administered once or more.
- It has measurements of ADA (note of, a subject with the sample which baseline result is potential positive but confirmatory result is not available will be excluded) at both baseline and at least one post-treatment anti-drug antibody assessment.

Each sample from the subject is categorized based on the following definitions:

Sample ADA Status:

- Baseline ADA-positive sample: ADA is detected in the last sample before initiation of treatment
- Baseline ADA-negative sample: ADA is not detected in the last sample before initiation of treatment
- ADA-positive sample: After initiation of treatment, (1) an ADA detected (positive

seroconversion) sample in a subject for whom ADA is not detected at baseline, or (2) an ADA detected sample with ADA titer to be at least 4-fold or greater (\geq) than baseline positive titer

- ADA-negative sample: After initiation of treatment, ADA not positive sample relative to baseline (except missing data).

Next, using the sample ADA status, subject ADA status is defined as follows:

Subject ADA Status:

- Baseline ADA-positive subject: A subject with baseline ADA-positive sample. Among the baseline ADA-positive subjects, the subject who has baseline ADA-positive sample with neutralizing antibodies detected will be defined as the baseline neutralizing positive.
- ADA-positive subject: A subject with at least one ADA positive-sample relative to baseline at any time after initiation of treatment
 - Persistent Positive (PP): ADA-positive sample at 2 or more consecutive time points, where the first and last ADA-positive samples are at least 15 weeks apart
 - Not PP-Last Sample Positive: Not persistent positive with ADA-positive sample at the last sampling time point
 - Other Positive: Not persistent positive but some ADA-positive samples with the last sample being negative
 - Neutralizing Positive: At least one ADA-positive sample with neutralizing antibodies detected
- ADA-negative subject: A subject with no ADA-positive sample after the initiation of treatment.

The number (percentage) of subjects will be summarized by part for the following subject ADA status.

- Baseline ADA-positive
- ADA-positive
 - Persistent Positive (PP)
 - Not PP-Last Sample Positive
 - Other Positive
- ADA-negative

Subject data listing of all ADA assessments will be provided.

For exploratory purpose, the number (percentage) of subject with the baseline neutralizing positive/neutralizing positive may be summarized, if appropriate. Also, subject data listings of ADA assessments for subjects with neutralizing positive may be provided.

5.8 Exploratory Analyses

No exploratory analyses are planned for this study.

